3.3 Risk Analysis

CONTEXT OF THE PROPOSED INVESTIGATION:

Radiofrequency (RF) technology is commonly used in surgery, noninvasive treatments and aesthetic applications. RF technology is a safe method for non-ablative (A non-wounding device treatment which heats underlying skin) treatment because energy can be precisely delivered through the skin to the dermal tissue beneath without damaging the epidermis.

Aging skin shows decreased collagen synthesis and alteration of fiber networks. By gently heating dermis tissue (which is comprised of collagen, elastic fibers and ground substance), both immediate effects (collagen contraction) and long-term effects (wound-healing response with neocollagen production) will occur. RF-induced thermal injury to the dermal tissue will produce a microinflammatory response to induce collagen denaturation, contraction, and subsequent synthesis as well as elastin and ground substance production.³ This, in turn, creates a tightening effect that helps to eliminate facial wrinkles, and is also used for other cosmetic treatments on the body.⁴

The extent of collagen shrinkage, fibroblast activation, fibroplasia and neocollagenesis in the different skin layers is based on a complex multivariate mechanism, which depends on the temperature distribution and timing.² Further investigation of parameter optimization is necessary to achieve safe and efficacious results.

ASSESSMENT OF RISKS OF THE PROPOSED INVESTIGATION:

The risk identified with the overall clinical investigation is the integrity of the data collected. There are multiple clinical mitigation strategies for the risk identified. Proper training on the protocol will be performed. Monitoring of the study will be implemented to minimize subject and data risks.

ASSESSMENT OF BENEFITS OF THE PROPOSED INVESTIGATION:

The subject may or may not have improvement in their facial wrinkles.

CONSIDERATION OF PATIENT PREFERENCE INFORMATION:

Many physicians support the use of radiofrequency devices for non-invasive cosmetic treatments due to current patient satisfaction of cosmetic results with the currently available devices. However, there is still a level of interest in novel technologies that could reduce the need for future treatments.

ASSESSMENT OF UNCERTAINTY:

There is uncertainty of efficacy results while using the TempSure device in this study.

CONCLUSION:

This device is determined to be a non-significant risk study and will be using a handpiece not cleared for use by the FDA. The Icon device is cleared for use by the FDA but may not be used within its currently cleared instructions for use. The risks posed to the subjects and integrity of data are acceptable.

Patient population to be enrolled in this clinical study:

Total anticipated population: 50 Subjects

Age Range: 18 years of age or older

Gender: Male or Female

Condition: Facial Wrinkles (TempSure) and benign pigmented and/or vascular lesions (Icon)

4.0 DEVICE DESCRIPTION AND SPECIFICATIONS

The TempSure® device used in this study is currently cleared by the U.S. Food and Drug Administration (the FDA). The TempSure® device received 510(k) clearance under K171262 on September 22, 2017 for:

- The 10mm, 15mm, and 20mm TempSure Envi handpieces are indicated for non-ablative treatment of mild to moderate facial wrinkles and rhytids.
- The 18mm, 25mm, and 30mm TempSure Envi handpieces provide heating for the purpose of elevating tissue temperature for selected medical conditions such as temporary relief of pain, muscle spasms, and increase in local circulation.
- The Massage device is intended to provide a temporary reduction in the appearance of cellulite.
- Coagulation/Hemostasis: Using the surgical handpieces and accessories, general surgical procedures including urologic, thoracic, plastic, reconstructive, and gynecological procedures where electrosurgical coagulation of tissue is performed.

And received 510(k) clearance under K182365 on October 24, 2018 for:

- Cutting: snoring, submucosal palatal shrinkage, traditional uvulopalatoplasty (RAUP),

myringotomy with effective hemorrhage control, epistaxis treatment, turbinate shrinkage, skin incisions, biopsy, cysts, abscesses, tumors, cosmetic repairs, development of skin flaps, skin tags and blepharoplasty.

- Blended Cutting and Coagulation: snoring, submucosal palatal shrinkage, traditional uvulopalatoplasty (RAUP), myringotomy with effective hemorrhage control, epistaxis treatment, turbinate shrinkage, skin tags, papilloma keloids, keratosis, verrucae, basal cell carcinoma, nevi, fistulas, epithelidma, cosmetic repairs, cysts, abscesses, and development of skin flaps.
- Fulguration: basal cell carcinoma, papilloma, cyst destruction, tumors, verrucae, hemostasis.
- Bipolar: pinpoint precise coagulation, pinpoint hemostasis in any field (wet or dry). Snoring, submucosal palatal, shrinkage, traditional uvulopalatoplasty (RAUP), myringotomy with effective hemorrhage control, epistaxis treatment and turbinate shrinkage

The 60mm handpiece (under K190678 on July 24, 2019) and FlexSure applicators (under K200241 on March 25, 2020) of the TempSure® device received 510(k) clearance to provide heating for the purpose of elevating tissue temperature for selected medical conditions such as temporary relief of pain, muscle spasms, and increase in local circulation.

Changes to the TempSure® device are anticipated during the investigation as the Mini Envi handpiece is expected to receive clearance for use from the FDA.

The TempSure® Device Specifications are:

Surgical Connector	1 surgical monopolar port
Neutral Connector	One universal neutral connector compatible with Cynosure neutral electrodes
Smart Handpiece Connectors	One 4-pin circular connector for both RF energy delivery and temperature sensing (monopolar)
Modes of Operation	Select the Smart Handpiece or Surgical mode of operation
Maximum Power	
Temperature-Sensing Handpieces
 
 ⚠ 10mm, 15mm, and 20mm handpieces have a maximum GUI setting of 70, which provides output power of 120 Watts (+/- 20%). ⚠ 18mm handpiece has a maximum GUI setting of 25, which provides output power of 25 Watts (+/-20%). ⚠ 25mm and 30mm handpieces have a maximum GUI setting of 80, which provides output power of 165Watts (+/- 20%). ⚠ 60mm handpieces have a maximum GUI setting of 100, which provides output power of 300 Watts (+/- 20%). ⚠ FlexSure applicators are controlled by setting the temperature. During treatment, power can reach a maximum output of 300 Watts (+/- 20%). 
Ensuring that the neutral pad recommended for use with the 60mm handpiece and flexible applicator has sufficient current carrying capacity so as to assure that there is no unacceptable temperature rise under the pad is an essential performance of the TempSure platform.

The TempSure® consumables are: Handpieces, NEM Pads

The Icon device used in this study is currently cleared by the U.S. Food and Drug Administration (the FDA). The Icon device received 510(k) clearance under K103664 on March 17, 2011 for:

The Max Series Intense Pulsed Light Handpieces are intended for the treatment of inflammatory acne (acne vulgaris) and for the treatment of benign pigmented epidermal and cutaneous lesions, including warts, scars and striae; removal of unwanted hair from skin types 1-VI, and to effect stable long-term, or permanent, hair reduction; treatment of benign pigmented lesions, including lentigines, nevi, melasma, and cafe-au-lait; and treatment of vascular lesions, including port wine stains, hemangiomas, angiomas, telangiectasias, rosacea, facial and leg veins.

The Icon Device Specifications for the Max G handpiece are:

The **MaxG™ Handpiece** is recommended for treatment of benign pigmented lesions and vascular lesions, e.g., telangiectasias, rosacea, port-wine stain, hemangioma, angioma, and spider veins, on skin types I-IV.

MaxG™ Pulsewidth (ms)	Minimum Fluence (J/cm²)	Maximum Fluence (J/cm²)	Fluence Increments
1	3	11	1
2	5	21	2
3	6	30	2
5	6	36	2
10	20	54	2
15	20	60	2
20	20	68	2
25	20	74	2
30	20	80	2
40	20	80	2
60	20	80	2
80	26	80	2
100	32	80	2

Handpiece	Spot size (mm)	Repetition Rate (Hz)	Spectral Range (nm)	Fluence Range* (J/cm²)	Application
	10 x 15	.2 – 2.0	500 – 670 & 870 - 1200	Up to 80	Pigmented and Vascular Lesions (skin types I-IV)

*The effective fluence may be higher due to photon recycling, wide spectrum, spot size, and skin contact. There is a ±7% maximum variation of the output from the mean value across the treatment area.
Ocular Hazard Distance = 3.3 meters.

5.0 MONITORING PROCEDURES

The Sponsor Standard Operating Procedure (SOP) for monitoring the investigative site will be followed. The sponsor will train the site following sponsor SOP's and may be present at initiation of treatment. The sponsor will also monitor the site periodically. The Investigator/Institution will permit trial-related monitoring, audits, IRB/IEC review, and regulatory inspections by providing direct access to source documents. The sponsor may request intermediate data following each visit to evaluate treatment progress. Case Report Forms will be reviewed for current data and Regulatory Binders will also be reviewed for correct documents. The sponsor will collect data at the end of the follow up period. The sponsor will list the study on clinicaltrials.gov when required by FDA regulations.

The monitoring plan for this study is outlined in the Cynosure Monitoring Plan.

ASSIGNED CLINICAL RESEARCH MONITOR:

Monitor #1
 Name: [name]
 Institution: Cynosure, LLC
 Address: [name]

6.0 LABELING

Sample labeling will follow FDA regulations and the sponsor standard operating procedure. If applicable, the TempSure® device label will include, (in accordance with 801.1):

Statement: "CAUTION--Investigational device. Limited by Federal (or United States) law to investigational use."

Additionally, the label or other labeling will describe all relevant contraindications, hazards, adverse effects, interfering substances or devices, warnings, and precautions.

Directions for use are contained in the TempSure® Operator's Manual

7.0 CONSENT MATERIALS

Forms and informational materials which are provided to the subject during the informed consent process are listed below:

Form/Informational Material Description
Pre and Post Treatment Instructions
Informed Consent Form

9.0 OTHER INSTITUTIONS

If a part of the study is conducted by an institution that has not previously been identified within the Investigational plan each institution’s contact information will be documented below;

No other institutions will be part of this study.

10.0 ADDITIONAL RECORDS AND REPORTS

If this is an IDE study, additional records and reports will be maintained on the investigation in addition to those prescribed in 21 CFR 812 sub-part G. If this is a non-IDE study, the study summary will be maintained on the investigation and may include those prescribed in 21 CFR 812 sub-part G.

Additional Records and Reports:

Report	Submit To	Description/Constraints
N/A	N/A	This is a non-IDE study; no additional records or reports will be maintained.

11.0 PREGNANCY

Females may not participate in this study if they are pregnant, breastfeeding, were pregnant within the last three months or are planning a pregnancy during the study.

If the subject thinks they have become pregnant during the study, it is important that they inform the Investigator immediately. If she becomes pregnant or thinks that she may be pregnant, she will be removed from the study and will be asked to perform a final evaluation similar to the final follow-up visit. The Investigator may request to track the pregnancy and will report the pregnancy to the Sponsor.

12.0 SUBJECT WITHDRAWAL

The subject is free to withdraw from this study at any time. The subject must inform the Investigator immediately if they intend to withdraw. To terminate the subject’s participation in this study, they

must contact the Investigator at the contact information listed on page one of the informed consent form. They will be asked to come to the study clinic or Investigators office to complete a final follow up visit and may be asked to perform end of study procedures. Their decision to participate in this study or to withdraw from this study will not influence the availability of their future medical care and will involve no penalty or loss of benefits to which they are otherwise entitled.

The Investigator in charge of the study can remove the subject from this study without their consent for any reason, including, but not limited to:

- a) His/her judgment that any condition or circumstance may jeopardize their welfare or the integrity of the study.
- b) Their failure to follow the instructions of the Investigator(s).
- c) If the study is stopped by the sponsor and/or Investigators participating in the study prior to completion.

Data collected prior to withdrawal will be used in data analysis but after withdrawal no further data will be collected.

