2.11 Replacement of Subjects

Replacement of subjects who have withdrawn or been withdrawn from the study will be allowed to be replaced with prior approval from the sponsor and/or IRB.

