2.14 Adverse Event Recording

All data captured must be supported by the Investigator’s timely assessment and documentation of the adverse event in the case report forms or source documents. All documented adverse events will be reviewed by the Sponsor or designee to determine whether the adverse event meets regulatory reporting requirements and to ensure timely adverse event reporting to meet local and global regulatory requirements. All adverse events must be followed until their resolution.

Adverse Events Pertaining to the TempSure Device:

Mild discomfort during treatment may be experienced by the subject. Typically, the discomfort is temporary and localized within the treatment area. Mild edema (swelling) and erythema (redness) may occur. Initial studies indicate that these side effects typically resolve within 2 to 24 hours.

Other anticipated side effects may include; pain, skin burns, bleeding, scarring, crusting, bruising, infection, itching, prolonged edema (swelling) and erythema (redness), hardness, and nodules. Loss of hair pigment may also occur within and adjacent to the treatment area.

Adverse Events Pertaining to the Icon Device:

Adverse effects can include discomfort/pain, redness, swelling, pinpoint bleeding, skin peeling, itching, scabbing, crusting, purpura, and bruising, which are usually transient and resolve without intervention.

Possible adverse effects include pustules (such as ingrown hairs), skin burns, hypopigmentation, hyperpigmentation, removal or lightening of freckles, scarring, infection and allergic reaction (such as a rash). There is also risk of incidental hair reduction or removal in the treated areas.

People of Middle Eastern and Mediterranean descent and those who have an ill-defined hair line with no obvious transition of the hairline to the face are at a high risk for hair stimulation (paradoxical hair growth).

Adverse Events Pertaining to Gel:

The gel is a water-based gel that may be placed on the skin during the TempSure® treatment. No known adverse events are documented. However, an allergic reaction is always possible when placing a topical gel onto the skin. Allergic reaction may include a mild reaction such as skin redness, irritation, or hives.

Adverse Events Pertaining to Neutral Pad:

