2.15.3 Patient Populations

Interim results may be collected and reported. All data will be analyzed at the end of the study. The primary analysis will be performed by the intention-to-treat approach. Everyone who begins the treatment is part of the study whether he or she completes the study or not. Additional per-protocol analysis may also be performed on subjects who complete the entire clinical trial according to the protocol. The most appropriate method of handling missing values will be chosen based on the individual trial goals, endpoints and context.

The analysis of demographic, medical history, and efficacy variables will be based on all patients who are randomized and receive at least one treatment. The analysis of safety data will be based on all patients who are randomized, receive at least one treatment, and have at least some safety data.

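### Section 12.0 stops data collection after withdrawal without separating withdrawal of consent from stopping treatment or removal by the investigator, and without excepting open adverse events

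*Combined protocol and SAP*

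**What the plan says.** Section 12.0 (Subject Withdrawal) covers two ways out of the study and ends with one data rule.

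- A subject may leave at any time and is then asked "to complete a final follow up visit and may be asked to perform end of study procedures".
- "The Investigator in charge of the study can remove the subject from this study without their consent for any reason". Failure to follow instructions and a stop of the study itself are among the examples.
- The section closes: "Data collected prior to withdrawal will be used in data analysis but after withdrawal no further data will be collected".

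Other sections bear on the same subjects.

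- 2.11 (Replacement of Subjects) uses one term for both routes: "Replacement of subjects who have withdrawn or been withdrawn from the study".
- 11.0 (Pregnancy) says of a subject who becomes pregnant that "she will be removed from the study and will be asked to perform a final evaluation similar to the final follow-up visit".
- 2.14 (Adverse Event Recording): "All adverse events must be followed until their resolution". Section 14.0 ends follow-up when the event has resolved, stabilised or been otherwise explained, or when the subject is lost to follow-up.
- 2.15.3 (Patient Populations) makes intention-to-treat primary: "Everyone who begins the treatment is part of the study whether he or she completes the study or not". It leaves the missing-data method to be chosen later.

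**The concern.** Stopping collection is right when a subject withdraws consent to it. A subject who only stops treatment, or whom the investigator removes, may be quite willing to come back for photographs. Section 12.0 has no separate provision for these subjects, so a site following its last sentence would stop collecting from them too.

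Two things are at stake. The first is the primary outcome, which compares baseline and 12-week images (1.2). In an open-label study (2.2), a discretionary removal that also ends outcome collection is an avoidable route to bias. The second is safety information. A subject who leaves with an open adverse event falls under one instruction to stop and another to continue, and the later course of that event may go unrecorded.

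**Working it through.** The point is mainly textual, so the sections are set side by side first.

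1. **12.0 against 2.14 and 14.0.** This is the most direct conflict. The stop in 12.0 has no safety exception. Section 2.14 runs follow-up to resolution. Section 14.0 adds stabilised, explained and lost to follow-up as end points. Neither lists withdrawal, and a withdrawn subject who can still be contacted is not lost to follow-up.
2. **12.0 against its own final visit, and against 11.0.** The section asks a departing subject to "complete a final follow up visit and may be asked to perform end of study procedures" and then bars further data. It never says when withdrawal takes effect. Section 11.0 places a final evaluation after removal. Whether final-visit photographs may be taken and used is therefore unclear.
3. **Does the stop cover removal by the investigator?** The sentence says withdrawal, not removal. However, it follows the list of removal reasons, no other general data rule covers removed subjects, and 2.11 speaks of subjects who have been withdrawn. Coverage is the natural reading, but it is an inference.
4. **12.0 against 2.15.3.** This is a conflict in effect, not in words. Non-completers who began treatment stay in the analysis set, while 12.0 stops collection of the image that the analysis uses. The zero-change rule in 2.15.5 is written for change scores and does not translate into a correct or incorrect identification.

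**Illustration of sensitivity to missing outcomes.** The plan states no withdrawal figure to reproduce; 2.15.2 gives 50 subjects including departures, with no rate.

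- Inputs from the plan: N = 50 (2.15.2) and a success threshold of 80% (2.15.1).
- Assumptions: m subjects lack a 12-week result, and each subject contributes one correct or incorrect result. The plan does not state the unit, and three reviewers grade the images.
- With all 50 counted, success needs 0.80 × 50 = 40 correct.
- Observed correct results needed among the 50 − m seen: 0.80 × (50 − m), rounded up, for complete cases; 40 if missing counts as not identified; 40 − m if missing counts as identified.

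| m (assumed) | Observed | Complete cases | Missing = not identified | Missing = identified |
|---|---|---|---|---|
| 3 | 47 | 38/47 = 80.9% | 40/47 = 85.1% | 37/47 = 78.7% |
| 5 | 45 | 36/45 = 80.0% | 40/45 = 88.9% | 35/45 = 77.8% |
| 10 | 40 | 32/40 = 80.0% | 40/40 = 100% | 30/40 = 75.0% |

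With m = 5 and 36 correct, the result is 36/45 = 80% (meets the threshold) among those observed, or 36/50 = 72% (does not) if missing counts as not identified.

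**The case against.** The strongest reply is that 12.0 is loosely worded, not contradictory. Subjects announce an intention to leave, contact the site and are asked for a final visit. Read in that order, the visit is the exit step and collection stops after it. Section 11.0 also suggests that the authors did not mean to bar data from removed subjects. This reading is possible, so the final visit is an ambiguity and not a proven contradiction. It still leaves the adverse event conflict, and it does not give removed subjects a 12-week photograph.

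Other parts of the reply stand, and they limit what can be claimed.

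- A reader might infer that the intention-to-treat analysis becomes impossible. It does not. Section 2.15.3 defines who is analysed, expects non-completers and missing values, and does not promise an image from everyone.
- A reader might infer that a subject who leaves because of a burn has no record of it. Section 14.0 requires events from the first treatment onward to be recorded, and its outcome codes include unchanged, unknown and lost to follow-up. What may be lost is the later course and final outcome.
- A reader might infer that subjects are removed for poor response. That is not among the examples in 12.0; only the open-ended wording would allow it.
- The table contrasts missing-data rules and would apply to any dropout. Subjects who refuse follow-up stay missing whatever 12.0 says.

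**Conclusion.** The point holds as a defect of scope. Section 12.0 does not separate withdrawal of consent from stopping treatment or removal, and it makes no exception for open adverse events. The conflict with 2.14 and 14.0 is clear on the text. The fit with the final visit in 12.0 and the evaluation in 11.0 is unclear. The effect on the primary analysis depends on reading the stop to cover removal, and it is a weakening through avoidable missing outcomes.

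The size cannot be estimated from the documents, because they give neither a withdrawal rate nor the share of departing subjects who would accept follow-up. The move from 80% to 72% rests on an assumed loss of 5 and one result per subject. It shows that missing outcomes in general can decide whether the threshold is met. It should not be read as the amount of bias caused by this sentence. The change is worth making because it is specific and cheap.

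**What to change.** - In 12.0, limit the stop to subjects who withdraw consent to further follow-up, and define that separately from stopping treatment and from removal by the investigator.
- Ask subjects who stop treatment or are removed, unless the study itself has ended, to attend the scheduled 4- and 12-week photographs and assessments. Sections 2.9 and 2.12 time these visits from the last treatment, so they are already defined for someone who stops early.
- Reconcile 12.0 with 2.14 and 14.0 on adverse events that are open at exit.
- State that the exit visit in 12.0 and the evaluation in 11.0 are collected. Use their photographs for the 12-week endpoint only if they fall within the 12-week window in 2.12 (plus or minus 1 week), and otherwise report them separately. Without this rule, early images would be mixed into the 12-week endpoint.

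The cost is a wording change in 12.0, matching consent wording if needed, and a few follow-up visits already in the schedule. Subjects who decline follow-up will still be missing, so the choice of missing-data method in 2.15.3 remains a separate matter.
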